#### **6.3.2 Final Study Visit (week 55 ± 14 days)**

A final study visit will be done approximately 1 month after the last dose, and the following procedures will be done:

1. Physical exam with vital signs.
2. Overview of medical/medication history.
3. Assessment of AEs.
4. Blood draw for clinical evaluations:
  - a. CBC/diff.
  - b. Acute care, hepatic, and mineral panels.
  - c. Serum tryptase
5. Pregnancy test (serum or urine, for participants of childbearing potential only).
6. Diary and memory aid review.

Participation in this study ends after this visit.

### 6.3.3 Early Termination Visit

All effort will be made to conduct an early termination visit for participants who withdraw from the study during the open-label treatment portion. This visit will include all of the procedures performed at the final study visit (see section 6.3.2).

### 6.4 Pregnancy

- If a participant becomes pregnant during the course of the study, then they will discontinue the study agent and research procedures but continue to be followed for safety assessments. There is a pregnancy exposure registry that monitors pregnancy outcomes in women exposed to KEVZARA during pregnancy. Pregnant women will be encouraged to register themselves by calling [name] and [[contact]](mailto:[contact]). If the study team is informed before a pregnant woman registers, the study team will enroll participant in pregnancy registry.

## 7 Study Procedures/Evaluations

**Blood draw:** Blood will be collected for clinical safety evaluations (CBC/diff; acute care, hepatic, and mineral panels; total protein; PT/PTT; lipids; serum tryptase; and CRP), storage, collection of DNA and RNA, and to examine serum IL-6 levels and markers of bone marrow resorption and deposition. Blood will also be used to test for HIV, hepatitis B, hepatitis C, and tuberculosis, to determine if the participant's blood cells carry the D816V mutation in the *KIT* gene, which is characteristic of adult ISM and for markers of ISM using flow cytometry. The amount of blood drawn for research purposes will be within the limits allowed for adult research participants by the NIH CC (Medical Administrative Policy 95-9, Guidelines for Limits of Blood Drawn for Research Purposes in the Clinical Center: <http://cc-internal.cc.nih.gov/policies/PDF/M95-9.pdf>).

**Bone marrow biopsy/aspirate:** Bone marrow specimens will be evaluated to determine if the participant's bone marrow carries the D816V mutation in the *KIT* gene and for evaluation of the extent of mast cell infiltration, markers, and morphology.

**Abdominal ultrasound:** Ultrasound of the participant's abdominal area will be conducted to evaluate enlargement of the liver and spleen.

**MC-QoL assessment:** The MC-QoL is a validated health-related QoL survey for adult patients with mastocytosis that consists of 27 items and is divided into four domains: symptoms, social life/functioning, emotions, and skin. The overall disease impairment on QoL is measured by assessing both the total score and the scores of each domain. The MC-QoL is provided in [Appendix C](#).

**SCORMA assessment:** SCORMA evaluates three measures of mastocytosis in a semi-quantitative fashion: extent of skin involvement, lesion activity, and subjective symptoms. The SCORMA chart is provided in [Appendix D](#).

**MSAS assessment:** The MSAS is used to evaluate a patient's experience with 32 symptoms over the course of the previous week. Symptoms are evaluated by severity and distress for eight of the symptoms, and also for frequency for the remaining 24. The MSAS is provided in [Appendix E](#).

**MQLQ/MSAF assessment:** The MQLQ is disease specific quality of life questionnaire validated in mastocytosis consisting of 49 questions to assess the effect of mastocytosis on daily life. It is complemented with the MSAF which is a symptom scoring form. The MQLQ is provided in [Appendix F](#) and the MSAF is in [Appendix G](#).

**Photographs:** Photographs will be taken at screening, at baseline before study drug is administered (optional), at the treatment peak, and at the post-treatment visit, and may also be taken at other visits to document physical findings. Identifiable photographs will be kept in a secure database. Participants will sign the standard NIH photography consent form before photos are taken.

**Skin punch biopsy (optional) :** The biopsy site may be numbed using a cream or spray before a local anesthetic is injected. A small circle of skin (2-5 mm) will be removed using a punch and the area will then be closed with gel foam, steri-strips, or non-absorbable sutures and covered with a dressing.

Research evaluation on biopsies will include immunohistologic staining to detect the presence and number of mast cells and/or maculopapular cutaneous mastocytosis and may include genetic studies.

## 8 Potential Risks and Benefits

### 8.1 Potential Risks

**Sarilumab:** Adverse reactions (ARs) have been determined in clinical trials conducted primarily in patients with rheumatoid arthritis and on combination therapy with disease-modifying antirheumatic drugs (DMARDs, eg, Imuran, cyclophosphamide, and methotrexate). Our patients with ISM in general are not being treated with DMARDs. In clinical trials as reported in the package insert and summarized below and in [Table 1](#), the most frequent ARs (occurring in at least 3% of patients treated with sarilumab in combination with DMARDs) were neutropenia, increased liver enzymes, injection site erythema, upper respiratory infections, and urinary tract infections.

Premature discontinuation due to ARs occurred in 8%, 6%, and 3% of patients treated with sarilumab at 200 mg, sarilumab at 150 mg, and placebo, respectively. The most common ARs (greater than 1%) that resulted in discontinuation of therapy with sarilumab was neutropenia.

The most commonly reported infections (2%-4% of patients) were upper respiratory tract infections, urinary tract infections, and nasopharyngitis. The most frequently observed serious infections included pneumonia and cellulitis. There is a theoretical risk for tuberculosis activation or shingles reactivation.

Reports of GI perforation were primarily reported as complications of diverticulitis including lower GI perforation and abscess. Most patients who developed GI perforations were taking concomitant nonsteroidal anti-inflammatory medications (NSAIDs) or corticosteroids. The contribution of these concomitant medications relative to sarilumab in the development of GI perforations is not known.

Injection site reactions were reported in 7% of patients receiving sarilumab at 200 mg, 6% receiving sarilumab at 150 mg, and 1% receiving placebo. These injection site reactions (including erythema and pruritus) were mild in severity for the majority of patients and necessitated drug discontinuation in 2 (0.2%) patients receiving sarilumab.

**Table 1: Common Adverse Reactions in Adults with Moderately to Severely Active Rheumatoid Arthritis**

Preferred Term	Placebo + DMARD (N = 579)	Sarilumab 150 mg + DMARD (N = 579)	Sarilumab 200 mg + DMARD (N = 582)
Neutropenia	0.2%	7%	10%
ALT increased	2%	5%	5%
Injection site erythema	0.9%	5%	4%
Injection site pruritus	0.2%	2%	2%
Upper respiratory tract infection	2%	4%	3%
Urinary tract infection	2%	3%	3%
Hypertriglyceridemia	0.5%	3%	1%
Leukopenia	0%	0.9%	2%

Adverse reactions occurring in 2% or more in the 150 mg sarilumab + DMARD or 200 mg sarilumab + DMARD groups and greater than observed in placebo + DMARD. Pre-rescue, placebo-controlled population.

ALT = alanine transaminase; DMARD = disease-modifying antirheumatic drug.

### Laboratory Abnormalities

Decreased neutrophil count less than 1000/ $\mu$ L occurred in patients on combination therapy and occurred in 6% and 4% of patients in the 200-mg sarilumab + DMARD and 150-mg sarilumab + DMARD groups, respectively, compared to no patients in the placebo + DMARD groups. Decrease in ANC was not associated with the occurrence of infections, including serious infections. Decreases in platelet counts less than 100,000/ $\mu$ L occurred in 1% and 0.7% of patients on 200- and 150-mg sarilumab + DMARD, respectively, compared to no patients on placebo + DMARD, without associated bleeding events. Liver enzyme elevations in the pre-rescue placebo-controlled population (sarilumab + DMARD or placebo + DMARD) are summarized in [Table 2](#).

Liver elevation was not associated with clinically relevant increases in direct bilirubin or clinical evidence of hepatitis or hepatic impairment.

Lipid abnormalities (low-density lipoproteins, high-density lipoproteins, and triglycerides) were observed at 4 weeks after initiation of therapy with no additional increases observed thereafter.

**Table 2: Incidence of Liver Enzyme Elevations in Adults with Moderately to Severely Active Rheumatoid Arthritis**

	Placebo + DMARD N = 579	Sarilumab 150 mg + DMARD N = 579	Sarilumab 200 mg + DMARD N = 582
AST			
> 1× ULN to 3× ULN	15%	27%	30%
> 3× ULN to 5× ULN	0%	1%	1%
> 5× ULN	0%	0.7%	0.2%
ALT			
> 1× ULN to 3× ULN	25%	38%	43%
> 3× ULN to 5× ULN	1%	4%	3%
> 5× ULN	0%	1%	0.7%

Phase 3 placebo-controlled safety population through the pre-rescue period. ALT = alanine transaminase; AST = aspartate transaminase; DMARD = disease-modifying antirheumatic drug; ULN = upper limit of normal.

### Malignancies

In the 52-week placebo-controlled population, 9 malignancies (exposure-adjusted event rate of 1.0 event per 100 patient-years) were diagnosed in patients receiving sarilumab + DMARD compared to 4 malignancies in patients in the control group (exposure-adjusted event rate of 1.0 event per 100 patient-years).

### Other Adverse Reactions

Because sarilumab is a monoclonal antibody, there is the risk of allergic or anaphylactic reactions. The most frequent hypersensitivity reactions observed in clinical trials were rash at the injection site rash or other parts of the body and urticaria.

While there are no nonclinical data suggesting risks to fertility or embryofetal development, sarilumab has not been evaluated in pregnant humans. There is an unknown but potential risk for sarilumab to be excreted in human milk. Therefore, participants should not be pregnant, planning to become pregnant, or breastfeeding while participating in this study.

There may be additional risks of sarilumab that are currently unknown.

**Bone marrow biopsy/aspirate:** Bone marrow biopsy and aspirate are commonly performed medical procedures that are associated with low risk, which includes the potential for some bleeding or infection at the site that may or may not require antibiotic treatment. There is usually some pressure-like discomfort during needle insertion, and the procedure may also result in a bruise and/or some discomfort at the site or surrounding tissue for a day or two after the anesthetic wears off. Standard procedures will be followed for all bone marrow biopsies and aspirates to minimize pain and the possibility of infection from the procedure.

**Conscious sedation:** Participants may request conscious sedation in addition to local anesthesia for bone marrow biopsy and aspirate. Sedative drugs will be provided by experienced

anesthesiologists of the NIH CC and IV administered. Side effects from sedative medications include cardiovascular and respiratory depression, manifested by bradycardia, hypotension, respiratory acidosis, and apnea. Additional ARs reported with these drugs are stinging or pain at the injection site, hiccoughs, nausea, vomiting, postoperative drowsiness and headache, and hypersensitivity reactions. Participants will be closely monitored and appropriate countermeasures will be taken as necessary.

**Skin punch biopsy:** Pain or discomfort may occur during and after the biopsy, even with the use of the local anesthetic. There may be a mild burning sensation when the numbing medicine is injected into the skin. The anesthetic may irritate the skin or rarely cause an allergic reaction, which can be treated with medicine. There may be bleeding at the biopsy site, which would require application of pressure to stop the bleeding. Rarely, biopsy sites become infected. In certain individuals, the biopsy will heal with a keloid. This is more likely to occur if it has happened in the past.

**Blood draw and insertion of IV catheter:** The risks of drawing blood and inserting an IV catheter for administration of sedative drugs include pain, swelling, redness, bruising, bleeding, and, rarely, fainting or infection.

**Photographs:** Taking pictures of the face and body may be embarrassing to some people. These photographs may be published in medical journals, without identifying the participant. We will attempt to preserve the anonymity of the participant as much as possible, while providing the information needed to support the research being published. Participants may decline photographs or place restrictions on their use. Participants will be given the opportunity to discuss this with the investigator.

## 8.2 Potential Benefits

Participants may not receive any benefit from this study. There is the potential that a 16-week treatment regimen of sarilumab will alleviate or resolve symptoms related to ISM. The results of this study may improve the investigators' understanding of anti-IL-6 therapy as treatment for ISM.

## 9 Research Use of Stored Human Samples, Specimens, or Data

**Intended Use:** Samples, specimens, and data collected under this protocol may be used to study mastocytosis. Genetic testing may be performed in the future.

**Storage:** All the stored study research samples are labeled by a code that only the investigators can link to the participant. Samples are stored in LAD storage space, which is a secure facility with limited access. Data will be kept in password-protected computers. Only investigators or their designees will have access to the samples and data.

**Tracking:** Samples and data acquired under this protocol will be tracked using the CRIMSON database system.

#### **Disposition at the Completion of the Protocol:**

- In the future, other investigators (both at NIH and outside) may wish to study these samples and/or data. If the planned research falls within the category of “human subjects research” on the part of the NIH researchers, IRB review and approval will be obtained. This includes the NIH researchers sending out coded and linked samples or data and getting results that they can link back to their participants.
- At the time of protocol termination, samples will either be destroyed or, after IRB approval, transferred to another existing protocol. Data will be archived by the study team in compliance with requirements for retention of research records; alternatively, after IRB and study sponsor approval, the data may be either destroyed or transferred to another repository.

#### **Reporting the Loss or Destruction of Samples/Specimens/Data to the IRB:**

- Any loss or unanticipated destruction of samples (for example, due to freezer malfunction) or data (for example, misplacing a printout of data with identifiers) that meets the definition of a reportable event will be reported to the NIH IM IRB according to NIH Human Research Protections Program (HRPP) Policy 801.
- Additionally, participants may decide at any point not to have their samples stored. In this case, the PI will destroy all known remaining samples and report what was done to both the participant and to the IRB. This decision will not affect the individual participant’s participation in this protocol or any other protocols at NIH.

## **10 Data Sharing Plan**

Human data generated in this study will be shared for future research as follows:

- De-identified data in an NIH-funded or approved public repository.
- De-identified data in another public repository.
- Identified data in the Biomedical Translational Research Information System (BTRIS, automatic for activities in the CC) and the Genomic Research Integration System (GRIS).
- De-identified or identified data with approved outside collaborators under appropriate agreements.

#### **When will the data be shared?**

Data may be shared with Sanofi/Genzyme shortly before publication.

## 11 Remuneration Plan for Participants

All participants may be reimbursed for travel and lodging, as per the NIAID policy. Participants will not receive any other remuneration.

## 12 Assessment of Safety

### 12.1 Definitions

The NIAID Clinical Safety Office (CSO) is responsible for sponsor safety oversight of this study, and the definitions below comply with CSO requirements.

**Adverse Event:** An AE is any untoward or unfavorable medical occurrence in a human participant, including any abnormal sign (eg, abnormal physical exam or laboratory finding), symptom, or disease, temporally associated with the individual's participation in the research, whether or not considered related to the research.

**Adverse Reaction:** An AE that is caused by an investigational agent (drug or biologic).

**Suspected Adverse Reaction (SAR):** An AE for which there is a reasonable possibility that the investigational agent caused the AE. 'Reasonable possibility' means that there is evidence to suggest a causal relationship between the drug and the AE. An SAR implies a lesser degree of certainty about causality than AR, which implies a high degree of certainty.

**Serious Adverse Event (SAE):** An SAE is an AE that results in one or more of the following outcomes:

- death
- a life-threatening event (places the participant at immediate risk of death from the event as it occurred)
- an inpatient hospitalization or prolongation of an existing hospitalization
- a persistent or significant incapacity or substantial disruption of the ability to conduct normal life functions
- a congenital anomaly/birth defect
- based upon appropriate medical judgment, may jeopardize the subject's health and may require medical or surgical intervention to prevent one of the other outcomes listed in this definition (examples of such events include allergic bronchospasm requiring intensive treatment in the emergency room or at home, blood dyscrasias or convulsions that do not result in inpatient hospitalization, or the development of drug dependency or drug abuse).

**Unexpected Adverse Event:** An AE is unexpected if it is not listed in the investigator's brochure or package insert (for marketed products) or is not listed at the specificity or severity that has been observed. It is the responsibility of the IND sponsor to make this determination.

**Serious and Unexpected Suspected Adverse Reaction (SUSAR):** A SUSAR is an SAR that is both serious and unexpected.

**Unanticipated Problem:** A UP is any event, incident, experience, or outcome that meets all of the following criteria:

1. Unexpected (in terms of nature, severity, or frequency) given (a) the research risks that are described in the protocol-related documents, such as the IRB-approved research protocol and informed consent document, and (b) the characteristics of the participant population being studied; and
2. Related or possibly related to participation in the research (possibly related means there is a reasonable possibility that the incident, experience, or outcome may have been caused by the procedures involved in the research); and
3. Suggests that the research places participants or others (which may include research staff, family members, or other individuals not directly participating in the research) at a greater risk of harm (including physical, psychological, economic, or social harm) related to the research than was previously known or expected. (Per the IND sponsor, an AE with a serious outcome will be considered increased risk.)

**Unanticipated Problem that is not an Adverse Event (UPnonAE):** A UP that does not fit the definition of an AE, but which may, in the opinion of the investigator, involve risk to the participant, affect others in the research study, or significantly impact the integrity of research data. Such events would be considered non-serious UPs. For example, we will report occurrences of breaches of confidentiality, accidental destruction of study records, or unaccounted-for study drug.

**Protocol Deviation:** Any change, divergence, or departure from the IRB-approved research protocol.

1. Major deviations: Deviations from the IRB-approved protocol that have, or may have the potential to, negatively impact, the rights, welfare or safety of the subject, or to substantially negatively impact the scientific integrity or validity of the study.
2. Minor deviations: Deviations that do not have the potential to negatively impact the rights, safety, or welfare of subjects or others, or the scientific integrity or validity of the study.

**Non-compliance:** Failure of investigator(s) to follow the applicable laws, regulations, or institutional policies governing the protection of human subjects in research, or the requirements or determinations of the IRB, whether intentional or not.

1. Serious non-compliance: Non-compliance, whether intentional or not, that results in harm or otherwise materially compromises the rights, welfare and/or safety of the subject.

Non-compliance that materially affects the scientific integrity or validity of the research may be considered serious non-compliance, even if it does not result in direct harm to research subjects.

2. Continuing non-compliance: A pattern of recurring non-compliance that either has resulted, or, if continued, may result in harm to subjects or otherwise materially compromise the rights, welfare and/or safety of subjects, affect the scientific integrity of the study or validity of the results. The pattern may comprise repetition of the same non-compliant action(s), or different noncompliant events. Such non-compliance may be unintentional (e.g., due to lack of understanding, knowledge, or commitment), or intentional (e.g., due to deliberate choice to ignore or compromise the requirements of any applicable regulation, organizational policy, or determination of the IRB).

## 12.2 Documenting, Recording, and Reporting Adverse Events

All AEs occurring from the baseline visit through the final study visit will be documented, recorded, and reported.

At each contact with the participant, information regarding AEs will be elicited by appropriate questioning and examinations and will be:

- immediately documented in the participant's medical record/source document,
- recorded in CRIMSON, and
- reported as outlined below (eg, IND sponsor, IRB, and FDA).

If a diagnosis is clinically evident (or subsequently determined), the diagnosis rather than the individual signs and symptoms or lab abnormalities will be recorded as the AE.

A laboratory abnormality will not be reported as an AE if ALL of the following criteria are met:

- It is no more than "Grade 1" or "Mild" per the protocol-specified toxicity table (or investigator assessment if not listed on the table); AND
- It does NOT require an intervention (eg, discontinuation of treatment, dose reduction/delay, additional assessments, or treatment); AND
- It is assessed by the PI as NOT related to the study agent(s); AND
- It is assessed by the PI as NOT clinically significant (eg, the abnormal value does NOT suggest a disease or organ toxicity).

All abnormal laboratory findings will be reviewed on a routine basis by the PI to identify potential safety signals. An abnormal lab not included on the toxicity table should be assessed in a similar fashion to the criteria above.

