## **6.1 Screening (Days –60 to –2)**

Informed consent will be obtained before the following screening tests are conducted:

1. Physical exam with vital signs, including height and weight.
2. Medical history/medication overview.
3. Assessment of ISM symptoms.
4. Blood draw for clinical evaluations:
  - a. Complete blood count with differential (CBC/diff).
  - b. Acute care, hepatic, and mineral panels.
  - c. Serum tryptase.
  - d. Prothrombin/partial thromboplastin time (PT/PTT).
  - e. HIV test (anti-HIV-1/2 antibodies).
  - f. Hepatitis B and C antibody test, B DNA, and C RNA.
  - g. QuantiFERON Gold tuberculosis test.
5. Serum or urine pregnancy test (participants of childbearing potential only).
6. MC-QoL.
7. SCORMA.
8. MSAS.

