9. MQLQ/MSAF
10. Bone marrow biopsy and aspirate (if not done at NIH within the last 150 days on protocol 02-I-0277).
11. *KIT* D816V mutation analysis on bone marrow and blood (if not done at NIH within the last 150 days)
12. Flow cytometry on bone marrow and blood (if not done at NIH within the last 150 days).
13. Ultrasound of abdomen.
14. Photography of affected areas.

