## **6.2 Randomized, Double-Blinded, Placebo-Controlled Treatment Period**

### **6.2.1 Baseline (Days –2 to 0)**

After eligibility has been confirmed, participants will visit the NIH CC for baseline testing. Participants may be admitted as inpatients and will be randomized to receive sarilumab or placebo. The following procedures will then be done at baseline:

1. Physical exam with vital signs.
2. Overview of medical/medication history.
3. Assessment of baseline symptoms of ISM.

4. Assessment of AEs.
5. Blood draw for clinical evaluations:
  - a. CBC/diff.
  - b. Acute care, hepatic, and mineral panels.
  - c. PT/PTT.
  - d. Total protein.
  - e. Lipid panel.
  - f. Serum tryptase.
  - g. C-reactive protein (CRP).
6. Urine or serum pregnancy test (for participants of childbearing potential only).
7. Blood draw for DNA and RNA collection.
8. Collection of serum (8 mL serum separator tube [SST]) for storage.
9. Serum IL-6 levels.
10. Serum markers of bone marrow resorption and deposition.
11. Plasma for storage (10 mL green top tube [GTT]).
12. Whole blood for storage (3 mL lavender top tube [LTT]).
13. MC-QoL.
14. SCORMA.
15. MSAS.
16. MQLQ/MSAF.
17. *KIT* D816V mutation analysis on blood.
18. Flow cytometry on blood.
19. Photography of affected areas (optional).
20. Skin punch biopsy (optional).

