AE = adverse event; HBV = hepatitis B virus; HCV = hepatitis C virus; IL = interleukin; ISM = indolent systemic mastocytosis; MC-QoL = Mastocytosis Quality of Life Questionnaire; MSAS = Memorial Symptom Assessment Scale; Q2W = once every 2 weeks; SCORMA = scoring of mastocytosis index; X = to be performed.

A Participants may be admitted as inpatients for this study visit. Procedures will be performed just once during this period.

B At the discretion of the study team, instead of coming to the NIH for study visits on weeks 6, 10 and 14, participants can self-administer study drug at home. No other procedures will be done at these time points for participants who self-administer.

C This visit will take 1-2 days as outpatients.

D Informed consent will be obtained before any study procedures are conducted on this protocol.

E Patients will be randomized to receive sarilumab or placebo.

F The screening physical exam will include measurement of vital signs, height, and weight.

G Sarilumab/placebo will be administered after the other study procedures have been completed.

H Will be done at screening only if not done within the last 150 days on protocol 02-I-0277 or this protocol.

I Only blood will be collected for *KIT* mutation analysis and flow cytometry at these visits.

j Optional at these visits.

k At visits 4, 6, 8, subjects may self inject at home. At these self administered injection timepoints, no assessments will occur.

	Open Administration Visits					Final Study Visit	Early Termination Visit
	Week 1 a	Week 7 ± 7 days	Week 19 ± 14 days	Week 31 ± 14 days	Week 43 ± 14 days	Week 55 ± 14 days	
Procedures/Evaluations							
Physical exam		X	X	X	X	X	X
Medical/medication history		X	X	X	X	X	X
AE assessment		X	X	X	X	X	X
CBC/diff		X	X	X	X	X	X
Acute care, hepatic, and mineral panels		X	X	X	X	X	X
Lipid panel		X		X			
Pregnancy test (serum or urine)		X	X	X	X	X	X
Serum tryptase		X	X	X	X	X	X
Diary review		X	X	X	X	X	X
Memory aid review		X	X	X	X	X	X
Study drug administration b	X	X	X	X	X		

AE = adverse event; CBC = complete blood count.  
 a Week 1 of the open administration portion of this study immediately follows the post-treatment visit.  
 b Study drug will be administered after all other procedures have been completed.

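### Adverse event recording opens at the baseline visit, although a marrow biopsy can be done on this protocol after consent and up to about 60 days earlier, so non-serious complications can go unrecorded and the start of SAE reporting is unclear

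*Combined protocol and SAP*

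**What the plan says.** Section 12.2 states the recording rule: "All AEs occurring from the baseline visit through the final study visit will be documented, recorded, and reported". In Appendix A the AE assessment row is blank at screening and first marked at baseline.

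Consent comes before screening. Section 6.1 says "Informed consent will be obtained before the following screening tests are conducted", and footnote D of Appendix A repeats the point. The 6.1 list then includes "Bone marrow biopsy and aspirate (if not done at NIH within the last 150 days on protocol 02-I-0277"; footnote H of Appendix A carries a similar waiver. Section 8.1 lists bleeding and infection among the risks of the procedure. It offers intravenous sedation to participants who ask for it, and says that side effects of the sedatives "include cardiovascular and respiratory depression, manifested by bradycardia, hypotension, respiratory acidosis, and apnea".

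The definitions in section 12.1 are wider than the recording window. An AE is any untoward occurrence linked in time to taking part in the research, "whether or not considered related to the research". Section 12.3 asks the investigator to judge relationship to the research as well as to the study agent.

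**The concern.** The plan treats harm from research procedures as an AE, but opens its AE record only after one of its more invasive procedures may already have been done. The same procedure at week 16 (section 6.2.4) falls inside the window, and no reason is given for treating the two differently.

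What is at stake is oversight of participant safety before dosing. A complication in a person who fails screening or withdraws before baseline has no scheduled AE assessment at which it would be picked up. A site facing a serious event at, say, day -40 would have to decide for itself whether the sponsor's safety office expects a report.

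**Working it through.** The documents give no figure to reproduce on this point. The check is day arithmetic on the visit windows, followed by a comparison of the reporting rules.

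**Length of the interval**

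Inputs: screening is days -60 to -2 (section 6.1); baseline is days -2 to 0 (section 6.2.1). Interval = baseline day minus biopsy day.

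- Biopsy on day -60: -2 - (-60) = 58 days to the earliest baseline, and 0 - (-60) = 60 days to the latest.
- Biopsy on day -2: -2 - (-2) = 0 days, and 0 - (-2) = 2 days.

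The range is therefore 0 to 60 days. A marrow reused from 02-I-0277 may be older, but it was done under that protocol and is outside this point.

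**What each reporting route covers in that interval**

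- *AE recording (12.2, Appendix A).* The window opens at baseline. A non-serious complication that has resolved by then falls outside it. So does any non-serious complication in a person who never attends baseline. Section 12.2 also asks for AEs to be elicited at each contact, which could be read to include screening visits. However, the sentence before it sets the baseline start and the schedule has no screening assessment.
- *Baseline visit (6.2.1).* Examination, history and AE questioning could bring an ongoing or recent complication to light. This reaches only people who attend. The text does not say whether an event that began earlier becomes an AE or medical history.
- *SAE reporting (12.4.2, 12.9.3).* All SAEs go to the sponsor's safety office and to the DSMB, with no start date. But section 12.1 defines an SAE as a kind of AE, and 12.2 introduces the reporting sections as the place where its recorded AEs are passed on. One reading makes an SAE at day -40 reportable and the other does not.
- *Unanticipated problems (12.1, 12.4.3, 13.1).* No baseline start is stated, and harm from research procedures is included. The event must be unexpected given the risks in the protocol documents. The foreseeable complications are described in section 8.1, so in the nature and severity described there they would ordinarily not qualify.

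**Effect on the trial's results**

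The primary safety endpoint (section 3.2.1) is AEs during the randomized treatment period. Screening events precede any study agent, so the gap does not bias the comparison of arms. No sample size, power or alpha figure is involved.

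**The case against.** The strongest reply is that 12.2 and Appendix A agree with each other, so the baseline start is a consistent choice, and that serious events are covered elsewhere. Sections 12.4.2 and 12.9.3 do require all SAEs to be reported and give no start date. An infected biopsy site that is still active would also bear on eligibility, because section 4.3 excludes active infection, including localized infection. These points stand, and they limit the concern.

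A reader might infer that complications of the screening biopsy are never captured, or that a serious one could not reach the safety office or the DSMB. The documents do not support that. The SAE sections read on their own point the other way, unexpected problems have their own route, and the baseline visit may pick up what is still present.

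Nor do the documents support treating every enrolled person as exposed. The biopsy is waived when a recent one exists, sedation is optional, and section 4.1 recruits everyone from 02-I-0277 and says that they are also screened there. The share needing a marrow on this protocol could lie anywhere from none to all, and the documents give no expected number.

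The reply does not dispose of two things: resolved or pre-baseline non-serious complications have no AE record, and the SAE start date depends on which section is read first. Co-enrollment on 02-I-0277 does not settle the matter, because section 6.1 and footnote H provide for a marrow done on this protocol.

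**Conclusion.** The concern holds in a limited form. For anyone who has the biopsy on this protocol at screening, up to about 60 days can pass in which non-serious, foreseeable complications are not recorded as AEs, and in which the duty to report SAEs is ambiguous. This is a weakness in participant protection and safety reporting. It is not a flaw in the efficacy analysis or in the randomized safety comparison.

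The conclusion rests on reading 12.2 and Appendix A as written, and on the biopsy being done under this protocol and not carried over. The safety review and communications plan named in section 12.9.1 is not part of the documents. If it sets an SAE start date, the ambiguity would be smaller in practice, but the protocol text would still need to match.

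**What to change.** Amend section 12.2 so that SAEs, and AEs related to a procedure of this protocol, are recorded and reported from signature of consent, keeping the present baseline start for every other AE. State the same start date in section 12.4.2. Add an AE/SAE mark in the screening column of Appendix A, applying also to people who are screened and not randomized. List pre-dose events separately, so that the tabulation by arm for the randomized period is unchanged.

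The cost is a short text change in two sections, one table mark, one extra listing and a few additional pre-randomization event reports.
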